2.3 Primary endpoint

The primary endpoint is the change from baseline in HbA_{1c} 16 weeks after randomisation.

Primary analysis

1) The primary estimand will be addressed by the below primary analysis based on all Subjects included in the FAS and using the in-trial observation period. Note that if Subjects withdraw consent to contribute additional information or are completely lost to follow-up, missing data will still occur. The primary analysis will be implemented as a statistical model using multiple imputations where the Subjects without any available HbA_{1c} measurements at scheduled visits will have their HbA_{1c} value imputed from the available information from the treatment the Subject has been randomised to. Note that this resembles in essence a mixed model of repeated measurements analysis, but Subjects without post-randomisation measurements contribute to the analysis, as the missing values will be imputed. The analysis will be implemented as follows:

- In the first step, intermittent missing values are imputed using a Markov Chain Monte Carlo (MCMC) method, in order to obtain a monotone missing data pattern. This imputation is done for each group separately and 100 copies of the dataset will be generated.
- In the second step, for each of the 100 copies of the dataset, an analysis of variance model with strata (two levels based on use of own CGM or not), previous insulin use (three levels: NovoRapid[®], Apidra[®] (insulin glulisine), Humalog[®] (insulin lispro) and region as factors, and baseline HbA_{1c} as a covariate is fitted to the change in HbA_{1c} from baseline to week 4 for each treatment group separately. The estimated parameters, and their variances, from these models are used to impute missing values at week 4 for Subjects in each treatment group, based on strata, previous insulin use, region and baseline HbA_{1c}.
- In the third step, for each of the 100 copies of the dataset, missing values at week 8 are imputed in the same way as for week 4. The imputations are based on an analysis of variance model with strata, previous insulin use and region as factors and baseline HbA_{1c} and change from baseline in HbA_{1c} at week 4 as covariates.
- This stepwise procedure is then repeated sequentially for week 12 and 16
- For each of the complete data sets, the change from baseline to week 16 is analysed using an analysis of variance model with treatment, strata, previous insulin use and region as factors, and baseline HbA_{1c} as a covariate.
- The estimates and standard deviations for the 100 data sets are pooled using Rubin's formula:

$$m_{MI} = \frac{1}{100} \sum_{i=1}^{100} m_i ,$$

$$SD_{MI} = \sqrt{\frac{1}{100} \sum_{i=1}^{100} SD_i^2 + \left(1 + \frac{1}{100}\right) \left(\frac{1}{100-1}\right) \sum_{i=1}^{100} (m_i - m_{MI})^2}$$

where m_i and SD_i are the estimated means and standard deviations for the 100 copies of the dataset, and m_{MI} and SD_{MI} are the pooled estimates.

- From m_{MI} and SD_{MI} , the 95% confidence interval for the treatment differences is calculated.

Non-inferiority of fast-acting insulin aspart will be considered confirmed if the upper boundary of the two-sided 95% CI is below or equal to 0.4% or equivalent if the p-value for the one-sided test of

$H_0: D > 0.4\%$ against $H_A: D \leq 0.4\%$,

is less than or equal to 2.5%, where D is the mean treatment difference (fast-acting insulin aspart minus NovoRapid[®]).

Note that as the anticipated number of Subjects discontinuing treatment, but not trial is low, imputations based on such Subjects will not be suitable.

Provided that the hierarchical testing allows, the evaluation of superiority will be based on the same statistical model, as the primary analysis 1). The associated sensitivity analysis that follows will investigate the robustness of non-inferiority and superiority (analysis 3b and 3c) as well.

Sensitivity analyses for the primary analysis addressing the primary estimand

All sensitivity analyses for the primary analysis addressing the primary estimand will use the in-trial observation period.

- 2) First the primary analysis in 1) will be repeated, but excluding all factors except from treatment from the multiple imputation and analysis of variance models while still including baseline HbA_{1c} as a covariate. This analysis will explore the influence of the different factors.
- 3) The primary analysis approach chosen for this trial relies on the assumption that missing data is missing at random (MAR). This assumption implies that the HbA_{1c} for Subjects leaving the trial, after their withdrawal, develops in a similar way as the HbA_{1c} for similar Subjects that remain in the trial (not necessarily on treatment) and had similar development of HbA_{1c} before withdrawal. The MAR assumption may be questionable for Subjects

withdrawing at own will. Therefore the statistical models using multiple imputation will be repeated with the following alterations:

- a) Imputations will be done from the treatment arm that the Subject was randomised to and a value of 0.4% (non-inferiority margin) is added to the change from baseline in HbA_{1c} at week 16 for Subjects randomised to fast-acting insulin aspart with an imputed value at week 16.²
- b) Missing values at week 16 will be imputed from the comparator arm (NovoRapid[®]). This will serve as a sensitivity analysis for the superiority analysis. It does not rely on the MAR assumption, but assumes that Subjects on fast-acting insulin aspart with an imputed value at week 16 switch to NovoRapid[®]. The imputation will be done such that the treatment effect diminishes gradually (conditional imputation).
- c) Missing values at week 16 will be imputed from the comparator arm (NovoRapid[®]). This will serve as a supplementary sensitivity analysis for the superiority analysis. It does not rely on the MAR assumption, but assumes that Subjects on fast-acting insulin aspart with missing value at week 16 switch to NovoRapid[®]. The imputation will be done such that the treatment effect diminishes immediately (unconditional imputation).

Analyses addressing the secondary estimand

All analyses addressing the secondary estimand will use the on-treatment observation period.

- 4) The secondary estimand will be analysed using the same statistical model using multiple imputations as the primary analysis in 1) except using the on-treatment observation period.
- 5) A tipping point analysis based on a statistical model using multiple imputation model similar to 1), using the on-treatment observation period, will be made. In this analysis observations for Subjects without a measurement are imputed based on the treatment arm they were randomised to and Subjects without a measurement in the fast-acting insulin aspart group are given a penalty. This is done to investigate the robustness of the conclusion in the primary analysis with respect to the MAR assumption and mimics a scenario where the HbA_{1c} of the Subjects without a measurement in the fast-acting insulin aspart group evolve less favourably than predicted. As a first step imputations will be done without penalty assuming MAR in the treatment group. Second, a penalty will be added to the imputed values for week 16 in the fast-acting insulin aspart group. This is done repeatedly, gradually increasing the penalty until the conclusion from the non-inferiority analysis no longer holds. This will serve as a sensitivity analysis for the non-inferiority analysis and the specific value of the penalty that changes the conclusion will be used to evaluate the robustness of the conclusion of the non-inferiority analysis.

- 6) A tipping point analysis based on a statistical model using multiple imputation, similar to 5) but with the modification that Subjects without a measurement that discontinued treatment due to non-eligibility (Subjects discontinuing fast-acting insulin aspart/NovoRapid[®] prematurely due to criteria 1, 2, 3, and 4) in the fast-acting insulin aspart group will not have a penalty added to the imputed values. These analyses are motivated by the fact that data from Subjects prematurely discontinuing fast-acting insulin aspart/NovoRapid[®] due to non-eligibility can reasonably be assumed to be missing completely at random.
- 7) The same statistical model using multiple imputations as the analysis in 4), but using the PP analysis set and analysed using the on-treatment observation period. This analysis will investigate the situation that Subjects might have deviated from the inclusion and exclusion criteria and will serve as sensitivity analysis for the non-inferiority analysis.

2.4 Secondary endpoints

2.4.1 Confirmatory secondary endpoints

If the effect of CSII treatment with fast-acting insulin aspart can be confirmed in the primary analysis, the trial also aims to confirm the superiority of CSII treatment with fast-acting insulin aspart, for a number of secondary confirmatory endpoints.

The steps used in the hierarchical testing procedure are as follows:

Step 1 (Primary analysis): HbA_{1c} non-inferiority of fast-acting insulin aspart versus NovoRapid[®]

Step 2: 1-hour PPG increment (meal test) superiority of fast-acting insulin aspart versus NovoRapid[®]

Step 3: HbA_{1c} superiority of fast-acting insulin aspart versus NovoRapid[®]

Step 4: 1,5-anhydroglucitol superiority of fast-acting insulin aspart versus NovoRapid[®]

Step 5: time spent in low IG (≤ 3.9 mmol/L [70 mg/dL]) superiority of fast-acting insulin aspart versus NovoRapid[®]

The primary estimand for the primary endpoint will be repeated for the confirmatory secondary endpoints, change from baseline in 1-hour PPG increment (meal test), change from baseline in 1,5-anhydroglucitol and change from baseline of time spent in low IG (≤ 3.9 mmol/L [70 mg/dL]) during CGM 16 weeks after randomisation. The analyses related to these estimands are defined below and will be used for the decisions to continue or not, throughout the hierarchical testing procedure. These analyses will be based on the FAS and use the in-trial observation period.

The secondary analysis 4) will also be repeated for the confirmatory secondary endpoints. The analysis will be based on the FAS and using the on-treatment observation period.

Change from baseline in 1-hour PPG increment 16 weeks after randomisation (meal test) (Step 2)

As the second step of the hierarchical testing procedure, change from baseline in 1-hour PPG increment 16 weeks after randomisation will be tested for superiority of fast-acting insulin aspart compared to Novo Rapid[®].

The 1-hour PPG increment will be analysed based on the laboratory measured values in the meal test, and is derived as the 1-hour PPG measurement minus the pre-prandial PG.

The 1-hour PPG increment endpoint will be analysed using the FAS and the in-trial observation period based on a multiple imputation technique where the change from baseline in 1-hour PPG increment at week 16 for subjects with missing value are imputed based on data from subjects in the NovoRapid[®] arm with non-missing values at week 16. Multiple copies (100 copies) of the full dataset will be generated by imputing missing values based on estimated parameters as follows:

- An analysis of variance model with strata (two levels based on use of own CGM or not), previous insulin use (three levels: NovoRapid[®], Apidra[®], Humalog[®]), and region as factors and baseline 1-hour PPG increment as covariate is fitted to the change from baseline in 1-hour PPG increment at week 16 for the NovoRapid[®] group only. The estimated parameters, and their variances, from this model are used to impute missing values using stochastic simulation at week 16 for subjects in both treatment groups in order to generate 100 complete datasets.
- For each of the complete data sets, the change from baseline to week 16 is analysed using an analysis of variance model with treatment, strata (two levels based on use of own CGM or not), previous insulin use (three levels: NovoRapid[®], Apidra[®], Humalog[®]), and region as factors, and baseline 1-hour PPG increment as covariate. The estimates and standard deviations for the 100 data sets are pooled to one estimate and associated standard deviation using Rubin's formula. From this, the pooled estimate and 95% confidence interval for the treatment difference are calculated.

The superiority will be assessed by comparing the upper limit of the 95% CI to 0. If the upper 95% CI is below 0 then superiority will be confirmed.

Change from baseline in HbA_{1c} 16 weeks after randomisation (Step 3)

The third step in the hierarchical testing is to confirm superiority of fast-acting insulin aspart compared to NovoRapid[®] with respect to HbA_{1c} 16 weeks after randomisation.

The confidence interval from the primary analysis 1) will be used to determine superiority. Superiority will be confirmed if the upper boundary of the two-sided 95% confidence interval of the mean treatment difference (fast-acting insulin aspart minus NovoRapid[®]) is below 0%.

Change from baseline in 1,5-anhydroglucitol 16 weeks after randomisation (Step 4)

Step 4 in the hierarchical testing procedure is to confirm superiority of change from baseline in 1,5-anhydroglucitol 16 weeks after randomisation with fast-acting insulin aspart compared to NovoRapid[®].

The change from baseline in 1,5-anhydroglucitol will be analysed using a model similar to 1), but with baseline 1,5-anhydroglucitol as a covariate.

Superiority will be confirmed if the upper boundary of the two-sided 95% confidence interval of the mean treatment difference (fast-acting insulin aspart minus NovoRapid[®]) is below 0.

Change from baseline of time spent in low IG (≤ 3.9 mmol/L [70 mg/dL]) during CGM 16 weeks after randomisation (Step 5)

The time spent in low IG is defined for each Subject at each CGM period as the accumulated time in hours spent below or equal to 3.9 mmol/L [70 mg/dL] from the first valid sensor value divided by the actual duration of the profile. To report the endpoint in minutes per 24 hours the ratio is multiplied by 1440.

Step 5 of the hierarchical testing procedure is to confirm superiority of change from baseline of time spent in low IG (≤ 3.9 mmol/L [70 mg/dL]) during CGM 16 weeks after randomisation with fast-acting insulin aspart compared to NovoRapid[®].

The change from baseline of time spent in low IG (≤ 3.9 mmol/L [70 mg/dL]) will be analysed with a model similar to 1), but with the corresponding baseline value as covariate.

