8.3.7 Meal test

UTN: U1111-1118-2480

EudraCT no.: 2010-024054-11

The Subject will undergo a standardised liquid meal test at certain visits (see section 2) and will have their 30 minute and 1 to 4 hour PPG measured. During that time 6 blood samples will be drawn, as specified in the Table 8–2. The samples will be analysed by the central laboratory and the values transferred directly into the trial database.

The Subject must attend the meal test visits in a fasting condition, as detailed in section 8.1.7. Bolus infusion and other medication which should be taken before, in a relation to or after a meal should be withheld until the meal test has been performed.

The Subject should before the meal test be instructed to:

- Follow normal routine regarding eating and exercise habits on the day prior to the meal test
- Refrain from intake of alcohol and use of medications that affect motility (i.e. prokinetics, anticholinergics, tricyclic antidepressants) on the day prior to the meal test, unless the Subject was on this medication at trial entry and does not change the product or product dose
- Not to make any changes in the current basal rate setting 4 hours prior to the meal test
- Measure a SMPG value at 4 AM the night before and in the morning before the meal test. The 4 AM SMPG value and before-meal-test SMPG value is part of the 9-point profile
- Change infusion set and reservoir in the morning the day before the meal test
- Continue to wear the CGM device until end of meal test
- Take a correction bolus according to guidance from Bolus Wizard® if the PG value above the target level

There should be a minimum of four hours between any correction bolus dose and the start of the meal test.

Protocol	1	Date:	04 February 2016	Novo Nordisk
Trial ID: NN1218-3854		Version:	4.0	

 Trial ID: NN1218-3854
 Version:
 4.0

 UTN: U1111-1118-2480
 Status:
 Final

 EudraCT no.: 2010-024054-11
 Page:
 67 of 149

Any hypoglycaemic episodes from midnight before the meal test should be treated and the hypoglycaemic episode should be recorded in the diary, please see section 8.3.3.1. In this case, the meal test should be re-scheduled within the visit window and at Visit 6 before randomisation to trial product.

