The Subject should have SMPG values within a range of 4.0-8.8 mmol/L [71-160 mg/dL] before beginning the meal test and bolus insulin dosing. The SMPG values should be verified and recorded at the site before starting the meal test. If the Subject is not fasting or the SMPG value is outside the range, the meal test should be rescheduled within the visit window.

At randomisation (Visit 6) the Investigator must evaluate the Subjects' eligibility to continue in the trial before the meal test is performed. Only Subjects eligible for randomisation should have the Visit 6 meal test performed. Thus, this assessment should not be performed for run-in failure Subjects. Randomisation (Visit 6) should not take place until the meal test has ended.

The Subject's body weight must be measured and a blood sample must be drawn two minutes before intake of the standardised liquid meal. The bolus insulin dose should be calculated by the Investigator based on the dose level of 0.1 unit/Kg body weight. The calculated dose should be rounded to the nearest whole unit. The 0.1 unit/kg dose is chosen as an approximation of a clinically relevant bolus dose needed for the given size of a standardised meal for T1DM. Only a normal bolus type is allowed. The Investigator must review the pump settings before the start of the meal in accordance to section 8.3.2.1. The start of bolus infusion will be defined as time point 0. The Subject will have a carbohydrate-rich standardised meal served immediately after bolus infusion and must consume this as quickly as possible (within 12 minutes). The Investigator should confirm that the Subject consumed the required volume of the standardised liquid meal in the eCRF and actual clock time of start of infusion and meal consumption should be noted.

The standardised meal will be provided by Novo Nordisk. The volume of the standardised meal to be consumed should be measured out by the Investigator to be the equivalent to 78 grams of carbohydrate.

Trial ID: NN1218-3854
UTN: U1111-1118-2480
EudraCT no.: 2010-024054-11

CONFIDENTIAL

CONFIDENTIAL

CONFIDENTIAL

CONFIDENTIAL

CONFIDENTIAL

Page: 68 of 149

Table 8–2 Meal test for Visit 6 and Visit 22

Time point – minutes	Bolus insulin infusion / Standardised meal	Blood sample (PG)*	SMPG values
Before start of meal test			X (within target range 4.0-8.8 mmol/L [71-160 mg/dL])
-2		X	
0	X		
30		X	V (as appropriate to ensure
60		X	X (as appropriate to ensure Subject's safety)
120		X	Subject's surety)

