For endpoints measured over time, mean values will be plotted to explore the trajectory over time. For survival endpoints (e.g. drop-out pattern) Kaplan-Meier plots are presented for each treatment.

Data collected before randomisation (Visit 6) will only be summarised descriptively.

Subjects that prematurely discontinue from treatment or withdraw from trial will attend end of treatment visits called visit 22A and 22B. Data collected at these visits will be reallocated to the next scheduled visit where the given assessment is planned. As a general rule, all observed values from randomised subjects will be used in all statistical analyses, but in case two different values are associated to the same visit in time, the use of a given value will depend on the estimand of interest. For the primary estimand the reallocated on-treatment value will not be used and for the secondary estimand the reallocated on-treatment value will be used. The estimands will be defined in the next section.

Testing strategy and estimands

The primary objective, to confirm the effect of CSII treatment with fast-acting insulin aspart in terms of glycaemic control by comparing it to CSII treatment with NovoRapid[®], in adults with T1DM, will be assessed by the change from baseline in HbA_{1c} using a non-inferiority approach.

More specifically the upper limit of the 95% confidence interval for the difference between fast-acting insulin aspart and NovoRapid[®] should be compared to a non-inferiority margin of 0.4%. If it is below or equal to 0.4% non-inferiority will be considered established and effect demonstrated.

The trial also aims to compare CSII treatment with fast-acting insulin aspart to NovoRapid[®] for a number of confirmatory secondary endpoints. The family-wise type I error rate will be controlled in the strong sense using a hierarchical (fixed sequence) testing procedure for the primary estimand. This is based on a priority ordering of the null-hypotheses, and testing them in this order using the two-sided 95% confidence interval approach until an insignificant result appears. The effect is that rejection of a null hypothesis only will be considered for analyses where all previous null-hypotheses have been rejected in favour of fast-acting insulin aspart.

The steps in the hierarchical testing procedure are as follows:

Step 1 (Primary analysis): HbA_{1c} non-inferiority of fast-acting insulin aspart versus NovoRapid[®]

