2.1 Sample size calculation

The primary objective of the trial is to confirm the effect of CSII treatment with fast-acting insulin aspart in terms of glycaemic control by comparing it to CSII treatment with NovoRapid[®] in adults with T1DM, using a non-inferiority approach. The non-inferiority margin of 0.4% (absolute) was chosen as described in section 5.2.1 of the protocol. The statistical evaluation will be done as described in section [2.3](#).

The trial also aims to confirm superiority of CSII treatment with fast-acting insulin aspart for a number of secondary confirmatory endpoints using the hierarchical testing procedure as described in section [2](#) (General considerations).

The sample size is determined to ensure sufficient power for the first step and second step in the hierarchical testing procedure.

In previous exploratory trials where CSII treatment with faster aspart has been investigated, the completion rates have been high. Therefore it is expected that treatment discontinuation might be as low as 4% where trial discontinuation constitutes half of these.

The power for the non-inferiority step is based on a t-statistic under the assumption of a one-sided test of size 2.5 %. A mean treatment difference of -0.1% for the comparison between fast-acting insulin aspart and NovoRapid[®] is expected. As trials in this population where Subjects are using insulin pumps and where data from treatment withdrawn subjects is retrieved are limited, a conservative estimate of the standard deviation (SD) in change from baseline in HbA_{1c} of 0.8% was chosen.

For determination of power in the second step in the hierarchical testing, where change from baseline in 1-hour PPG increment 16 weeks after randomisation is compared between fast-acting insulin aspart and NovoRapid® a t-statistic with a two-sided test of size 5.0% is used, where the treatment difference is expected to be at least 0.9 mmol/L [16 mg/dL]. The SD=3.4 mmol/L [62 mg/dL] in change from baseline in 1-hour PPG increments 16 weeks after randomisation based on laboratory analysed plasma glucose (PG) in a standardised meal test is considered reasonable, based on prior trials.

The power calculation is done using proc power in SAS Version 9.4. Please refer to [Table 2-1](#) for assumption of the sample size calculation.

Table 2-1 Specifications assumed for sample size calculation

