For each Subject this is calculated as the total number of infusion sets used divided by the actual duration of the randomised treatment period in days, multiplied by seven. It will be summarised for each treatment using descriptive statistics.

Number of Subjects with at least one non-routine change categorised by reasons for change

The percentage of Subjects with at least one non-routine change will be presented, categorised by reasons for change, in a frequency table by treatment.

3 Changes to the statistical analyses planned in the protocol

General considerations

It has been clarified how data collected at visit 22A and 22B are handled.

Statistical analysis

It has been clarified that type 1 error will only be controlled for the primary estimand.

In the sensitivity analysis 2) for change from baseline in HbA_{1c} it has been clarified that baseline HbA_{1c} is still included in the analysis as a covariate.

In the statistical analysis in the protocol it is not clear if missing values or values for subjects discontinuing treatment/withdraw from trial should be imputed. Some of the following changes have been implemented to account for this issue.

In the sensitivity analysis for change from baseline in HbA_{1c} it has been changed from subjects withdrawing from trial to subjects with an imputed value at week 16 to be aligned with the primary analysis.

In the statistical sensitivity analysis 3b) for change from baseline in HbA_{1c} copy reference has been changed to conditional imputation, and for 3c) jump to reference has been changed to unconditional imputation to clarified the method used.

It has been clarified that the statistical analysis 4) will be repeated as for the confirmatory secondary endpoints.

For change from baseline in 1-hour PPG increment (meal test) it has been clarified how the endpoint is derived, which is aligned with the other endpoints derived from the meal test. To align with the primary analysis it has been changed so values at week 16 are imputed for subjects with missing values instead of imputing values for subjects withdrawn from trial, and the imputations are based on subjects in the NovoRapid[®] arm with non-missing values instead of completers in the NovoRapid[®] arm.

For the statistical analysis of change from baseline of time spent in low IG (≤ 3.9 mmol/L) it has been clarified that the corresponding baseline value will be included as covariate.

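### Should missing week-16 meal tests of subjects still on faster aspart be imputed from the NovoRapid arm in step 2 of the hierarchy?

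*SAP*

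**What the plan says.** SAP 2.4.1 sets out step 2. An analysis of variance model is fitted to the NovoRapid group alone, and its parameters are used to fill missing week-16 values in both arms. The imputation applies "for subjects with missing value are imputed based on data from subjects in the NovoRapid[®] arm with non-missing values at week 16". Nothing separates subjects on product from those who stopped.

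The donor arm is inherited. Protocol 17.4.1 already fits the step 2 model to NovoRapid only. On who is imputed the protocol was ambiguous: its lead sentence names withdrawn subjects, while its first bullet names missing values in both groups. SAP section 3 settles this by recording that "values at week 16 are imputed for subjects with missing values instead of imputing values for subjects withdrawn from trial", to align with the primary analysis.

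The other confirmatory steps differ. In the primary analysis (SAP 2.3) missing HbA1c is "imputed from the available information from the treatment the Subject has been randomised to". Step 3 reuses that confidence interval, and steps 4 and 5 use a model similar to analysis 1). For HbA1c, NovoRapid-based imputation appears only in sensitivity analyses 3b and 3c; the SAP says of 3b that it "assumes that Subjects on fast-acting insulin aspart with an imputed value at week 16 switch to NovoRapid".

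On early discontinuation visits 22A and 22B, SAP section 2 (General considerations) says: "Data collected at these visits will be reallocated to the next scheduled visit where the given assessment is planned".

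**The concern.** A subject can reach Visit 22 on faster aspart, give an HbA1c sample and still have no meal test. Protocol 8.3.7 asks for the test to be moved when the entry conditions fail: "If the Subject is not fasting or the SMPG value is outside the range, the meal test should be rescheduled within the visit window". The same applies after overnight hypoglycaemia. The Visit 22 window in the flow chart is ±3 days. A subject who stops product early may have a Visit 22A test to carry forward; one who stays on product has only the rescheduled test.

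If that test is never done, step 2 gives the subject a NovoRapid-like value. By the SAP's own account of analysis 3b, such imputation stands for a switch to NovoRapid, and here no switch took place. The de facto estimand is repeated for this endpoint (SAP 2.4.1), so a value borrowed from the comparator is not what it asks for.

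Step 2 gates steps 3 to 5, its planned power of 80.0% leaves no slack, and nine supportive meal-test endpoints use a similar model (SAP 2.4.2.1). The stated alignment with the primary analysis covers who is imputed. It does not cover the donor arm, and no reason is given for that difference.

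**Working it through.** **Inputs.** SAP 2.1 gives 225 subjects per arm, SD 3.4 mmol/L, a difference of 0.9 mmol/L and a two-sided 5% test. The rate of missing meal tests is not given. I assume a share p in each arm, all still on product, which makes the loss as large as it can be for that p.

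**Plan's own figure.** A two-sample noncentral t-test with these inputs gives 80.0%, as stated. That figure allows for no missing data.

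**NovoRapid donors.**
- Expected difference: 0.9(1−p)
- Variance used by Rubin's rules: 2·SD²(1+p)/225
- True sampling variance: 2·SD²(1−p)/225
- Power: Φ[(0.9(1−p) − 1.965·√Rubin variance)/√sampling variance]

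At p = 4%: difference 0.864, Rubin SE 0.3269, sampling SE 0.3141. Then (0.864 − 1.965 × 0.3269)/0.3141 = 0.705, and Φ = 76.0%.

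**Own-arm donors.** The difference stays at 0.9, with a t-test on 225(1−p) per arm.

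| p | Difference, NovoRapid donors | Power, NovoRapid donors | Power, own-arm | One-sided null rejection, NovoRapid donors |
|---|---|---|---|---|
| 2% | 0.882 | 78.1% | 79.2% | 2.25% |
| 4% | 0.864 | 76.0% | 78.4% | 2.04% |
| 5% | 0.855 | 74.9% | 77.9% | 1.94% |
| 10% | 0.810 | 68.8% | 75.7% | 1.49% |

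The null column is Φ[−1.965·√((1+p)/(1−p))]. A simulation of 40,000 trials with 30 imputations and Rubin pooling gave 78.0%, 75.7%, 75.2% and 68.1% power for NovoRapid donors, and 2.28%, 1.98%, 1.83% and 1.41% under the null.

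**Baseline adjustment.** Assume a baseline to week-16 correlation of 0.5 and equal variances. The residual SD is 3.4·√(1.5/2) = 2.94. Power at 2%, 4% and 10% is then 88.6%, 87.1% and 81.7% with NovoRapid donors, against 89.3%, 88.7% and 86.6% own-arm. The gap is slightly smaller.

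**Is own-arm closer to the truth?** Let the affected faster aspart subjects keep a share k of the 0.9 effect, with missingness in the NovoRapid arm at random. The true difference is 0.9(1−p) + 0.9kp.
- Own-arm estimates 0.9, too high by 0.9p(1−k).
- NovoRapid donors estimate 0.9(1−p), too low by 0.9pk.

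The two errors are equal at k = 0.5. Neither exceeds 0.9p: 0.018 mmol/L at 2%, 0.036 at 4%, 0.09 at 10%.

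**What there is to condition on.** In the flow chart, HbA1c and 1,5-anhydroglucitol are measured at weeks 4, 8, 12 and 16, and there is a CGM period before Visit 14. Analysis 1) imputes from these earlier post-baseline values. The meal test is scheduled only at Visits 6 and 22, plus 22A for those who stop. (Protocol 8.5.1.3 mentions one at Visit 14, but neither the flow chart nor Table 8–2 has it.) Own-arm imputation in step 2 would therefore rest on baseline and design factors alone.

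**The case for a change.** The strongest argument for a change is that it looks cheap and principled: own-arm donors for subjects on product, NovoRapid donors for those who stopped or withdrew, and the present rule kept as a sensitivity analysis. It needs one more model and no new data. It would also bring the main estimate closer to the de facto estimand for people who never left faster aspart. As an account of the text this stands, and the power loss runs in the direction claimed.

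The remedy is weaker than it appears.
- It exchanges a conservative assumption for missing at random, with no interim meal test to support it. The entry conditions of Protocol 8.3.7 make some missing tests glycaemia-related, so low values of k cannot be excluded.
- It would loosen the test that opens steps 3 to 5, in the sponsor's favour, and depart from the protocol's model.
- The planning rates are no guide to how many subjects are affected. The SAP's "it is expected that treatment discontinuation might be as low as 4% where trial discontinuation constitutes half of these" describes the subjects for whom the remedy would keep NovoRapid donors.
- The group may be very small. SAP section 2 uses all observed values as a general rule, and no clause discards a test done outside the glucose range. A missing value on product therefore mainly means a test not done or a sample lost.
- Analysis 4) is repeated for this endpoint (SAP 2.4.1). It uses the primary model, so its natural reading is own-arm, although it covers the on-treatment period and does not drive the hierarchy.

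**Conclusion.** The concern is right about what the plan does, but the plan need not change. Step 2 uses a protocol-specified donor rule that biases against superiority, does not inflate type I error, and can be defended because there is no intermediate meal test to inform an own-arm model. The SAP does not give that reason; it is an inference from the visit schedule.

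The cost is about 1 point of power at 2% missing on product and about 2 points at 4%. It reaches 5 to 7 points only at 10%, a rate nothing in the documents suggests. These figures assume equal missingness in both arms and that every missing subject is on product. Whether own-arm imputation would be more accurate depends on k exceeding 0.5, which cannot be settled from the documents. What remains is a missing sentence on why the donor arm differs and on how analysis 4) is repeated for step 2. Analysts can settle both sensibly from the existing text, and neither affects the confirmatory result.
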